4.3.2 Inclusion criteria for community controls

Enrollment of community controls will not be restricted with respect to signs of non-severe pneumonia or presence of upper respiratory tract infection (URTI) symptoms. Analyses will be conducted both including and excluding ill controls.

Controls must meet the following inclusion criteria for eligibility to enter into the PERCH study:

- Aged 28 days-59 months
- Lives in defined study catchment area stratum (may be defined as a village or distance zone from the hospital)
- Accompanied by written informed parental/guardian consent

4.3.3 Exclusion criteria for community controls

Controls must not have any of the following exclusion criteria:

- Discharged from hospital within the last 14 days
- Severe/very severe pneumonia
- <30 days from discharge date of previous enrollment as a case
- Admitted to a hospital within the past 30 days because of an acute illness (in South Africa and Zambia only. CD4 counts will be done on HIV-infected community controls in these sites and an acute illness within the last 30 days may affect these results)

4.3.4 Rationale for HIV infected controls

Because of the very increased risk of pneumonia among HIV-infected children, it is expected that the cases will be disproportionately HIV-infected compared to the community. In the sites with high HIV prevalence (i.e. Zambia and South Africa), this might result in up to half of cases being HIV-infected. The community prevalence of HIV infection in children < 5 years, even in these high prevalence areas, will likely be <5%. Therefore, this will lead to an over-representation of HIV-infected cases compared with controls. This is the principle upon which to estimate the magnitude of the association between HIV and pneumonia. However, it is expected that the etiologic spectrum of respiratory pathogens will differ in HIV-infected children as will the pathogens colonizing the nasopharynx. An unconfounded analysis of the causal association between nasopharyngeal infection and pneumonia needs to compare HIV-infected cases with HIV-infected controls. To achieve sufficient numbers of HIV-infected controls to enable this comparison, a separate sampling strategy has been designed to enroll HIV-infected controls in these two sites.

HIV-infected controls will be enrolled from HIV patient support centers (PSC) serving the hospital catchment population. PSCs include ARV/ART clinics. We considered enrolling

hospitalized HIV-infected control subjects but rejected this option because of a 2-3 day lag-time in making the HIV diagnosis, by which time the naso/oropharyngeal flora will likely have become altered with nosocomially –acquired pathogens. Secondly, infants who are HIV-infected and admitted with non-pneumonia diagnoses have been difficult to find in South Africa due to improved prevention-of –mother –to-child-transmission and lower prevalence of HIV among newborns.

In Zambia and South Africa, HIV-infected controls will be enrolled in a 1:1 ratio with HIVinfected PERCH cases using the same age frequency matching approach described in section 4.3.7.

4.3.5 Inclusion criteria for HIV infected controls

HIV infected controls must meet the following inclusion criteria for eligibility to enter into the PERCH study:

- Documented to be HIV-infected
- Aged 28 days-59 months
- Screened at a PSC, either as follow-up or as a new patient, located in the catchment area from which the cases are being enrolled.
- Lives in defined study catchment area stratum (may be defined as a village or distance zone from the hospital)
- Accompanied by written informed parental/guardian consent

4.3.6 Exclusion criteria for HIV infected controls

Controls must not have any of the following exclusion criteria:

- Discharged from hospital within the last 14 days
- Severe/ very severe pneumonia
- Admitted to a hospital within the past 30 days because of an acute illness
- <30 days from discharge date of being previously enrolled as a case, or within the previous 3 months as a control
- Requires hospitalization on the day of admission

4.3.7 Matching and selection/sampling methods

Controls will be frequency matched on age and season to the cases to ensure that neither factor can confound the primary analysis, i.e. – the association between case-status and infection of the nasopharynx with respiratory pathogens.

Age strata for frequency matching to be used are the following: 28 days-5 months, 6-11 months, 12-23 months, 24-59 months. Seasonality matching will be done by month – attempts will be made to enroll the same number of cases and controls by month, with a minimum number of 25 controls per month. All analyses will incorporate stratification of age and season.

4.3.8 Case-control transitions

The following rules will be applied for case-control transitions:

a. Case-to-case. A case can be enrolled as a case again if admitted >30 days after -date of discharge from the hospital for an admission for which the child was enrolled in PERCH study and >14 days after the discharge from the last hospital admission (any cause). The 30 day limit is to ensure that the same pneumonia episode is not

enrolled twice and the 14 day limit is to avoid enrollment of nosocomial pneumonias.

- b. Case-to-control. To be consistent in the treatment of cases and controls, a previous case can be enrolled as a control if the control enrollment date is >30 days after the last PERCH date of discharge from the hospital for an admission for which the child was enrolled in PERCH study.
- c. Control-to-control. A control can be enrolled a second time as a control if selected through the random selection process-. There is no time period of exclusion between control selections.
- d. Control-to-case. A control can be enrolled as a case at any time after he/she was enrolled as a control. However, if he/she is enrolled as a case within 48 hours of being enrolled as a control, he/she would be excluded as a control from the recent control enrollment. The reason for this is that any URTI that the child had at the time of control enrollment might have been the early stage of the severe or very severe pneumonia.

Study sites will track study participants with a unique identifier to link separate episodes when they become eligible as cases or controls.

4.4 Control evaluation

To correctly classify the pneumonia status of enrolled controls, respiratory symptoms will be assessed at the time of screening and enrollment. Parents of controls will asked about the child's history of cough and difficulty breathing and will be questioned about the symptoms of upper respiratory tract infection (i.e. cough, runny nose, sore throat). Those with a history of cough or difficulty breathing will be examined by the fieldworker to determine the temperature, respiratory rate and presence of lower chest wall indrawing. If a child has lower chest wall indrawing, he/she will not be enrolled as a control and will be referred for clinical care. If the child has elevated respiratory rate for age (\geq 60 for under 2m, \geq 50 for 2-11m, \geq 40 for children under 5y - WHO definition), he/she will be enrolled as a control (and have control samples taken) and will then be referred by the field worker for evaluation at the hospital where cases are being enrolled. Referred controls will be identified at the study hospital and if they are considered by the clinical staff to have severe or very severe pneumonia, they will be given the opportunity to enroll as a case instead of as a control. Control children with URTI only will be instructed to present themselves to the PERCH hospital if their illness progresses. If upon evaluation of the child at the PERCH hospital, they are deemed to have severe or very severe pneumonia within 48 hours of their enrolment as a control, they will be invited to enroll as a case instead of as a control. If they are diagnosed with severe or very severe pneumonia more than 48 hours after their enrolment as a control, they will be eligible to be enrolled as a case but will also be maintained in the database as a control (they will be enrolled as both a case and a control). When > 48 hours have elapsed between control enrolment and pneumonia diagnosis, the preceding "control" URTI will be considered as a separate episode from the "case" pneumonia since as URTIs often precede pneumonia.

At the analysis stage, analyses will be conducted both including and excluding controls with evidence of URTI or non-severe pneumonia. Controls with URTI (i.e. cough, runny nose, sore throat, etc) and non-severe pneumonia (i.e. cough/difficulty breathing and elevated respiratory

rate) will be used to assess whether the prevalence of pathogens exists along a spectrum between asymptomatic, URTI and LRTI patients.

4.4.1 Lab tests/specimens collected

At the time of recruitment, controls will have three sets of specimens collected (below). Methods for collection are described in Section 4.5

- Upper respiratory swabs— one each of the following: a flocked swab from the nasopharynx, a rayon swab from the nasopharynx, and an oropharyngeal swab
- Blood 4 mL ideal, 2 mL minimum
 - Whole blood when possible either through venipuncture or fingerstick
- Urine 5 mL (when possible)

Table VIII. Control Specimens	
Body Fluid	Laboratory Analyses
Venous blood	Pneumococcus PCR
0-1kg: 3mL	HIV serology – Note: parents have the
≥1kg: 4mL	option to decline HIV testing. HIV positive
	participants will be referred for further
	clinical care (e.g. at an HIV patient support
	center).
	Singleplex PCR – HIV (subjects ≤18mo with
	positive antibody test)
	CD4 testing for HIV+ controls (in South Africa
	and Zambia only)
	Malaria (microscopy or antigen testing, in
	endemic areas)
	Sickle Cell Testing (Gambia, Mali, Zambia and
	Kenya)
	Thalassemia (Thailand only)
	Hemogoblin (Thailand and the Gambia only)
	Other Serology
	Storage for host genetic studies Biomarker testing
NP rayon swab	Bacterial culture for pneumococcus (and
	serotyping if applicable)
	serotyping in applicable)
Throat rayon swab/Flocked NP Swab	PCR for respiratory pathogens
Urine (5 mL)	Antibiotic activity testing (subset); storage for
	future testing (antigens; biomarkers)
	Total Urinary Arsenic testing (on a subset)
	Urinary Creatinine (on a subset)

4.4.2 Demographic and risk factors

Demographic and risk factor information will be the same as what is collected for cases. Refer to section 4.2.2.3.

4.4.3 Control follow-up

For tests that have clinical significance, the test results will be provided to the parents of control children. This will include results for HIV, CD4 counts, malaria, sickle cell, hemoglobin and thalessemia tests at applicable sites. Certain sites may also choose to provide the PCR results from the NP swab as required by the local IRB or local community feedback procedures. See table X (laboratory evaluations of controls) for more detail. Results that will be provided to controls will be specified in the site specific appendices.

If results are not immediately available (e.g. HIV PCR tests) at the time of control enrollment, the control child will be followed-up at the home or at the PSC to be given results and referred to appropriate ongoing care (e.g. HIV patient support center). The site of follow-up will be determined by each site according to local clinical practices.

4.5 Study subject evaluation methods

[figure not shown]
4.5.1 Specimen collection

4.5.1.1 Blood

Blood will be drawn from venipuncture in the amounts outlined above. Standard procedures for proper venipuncture will be employed, with particular attention to proper technique to minimize risk of contamination of blood cultures.

4.5.1.2 Nasopharyngeal swab

Two nasopharyngeal (NP) specimens will be collected from all cases and controls. One NP flocked swab will be collected and placed into viral transport medium, and a second flocked NP swab will be placed in skim milk tryptone-glucose-glycerin (STGG) medium.

4.5.1.3 Orpharyngeal swab

In addition to the NP swabs, all cases and controls will have an OP rayon swab collected and placed into the same vial of VTM as the NP flocked swab. The OP swab is taken by touching the swab to the posterior oropharynx and rubbing for 1-3 seconds.

4.5.1.4 Lung aspirates

Lung aspirates are very useful samples for determining pneumonia etiology, which can yield important information that guides patient therapy, but only a relatively small number of clinical

study sites have experience with this technique. The general technique used for pediatric lung aspiration is to insert a needle over the top of a rib into the area of consolidation or maximum physical findings, apply suction to the plunger of the syringe, maintaining constant suction while withdrawing the needle. Lung aspirates will be collected for clinical use and research; specimens will be tested in real time for clinical use purposes. Not all clinical sites will conduct lung aspirates; only those sites with sufficient site experience or physician experience will do this study procedure. Furthermore, only those children with large, peripheral consolidations that are amenable to lung aspirate will have the procedure conducted. Lung aspiration will not be performed on children with contraindications including: presence of pneumatocoeles on CXR, post measles pneumonia, patient is clinically unstable as determined by a clinician, CPR performed within the last 24 hours.

4.5.1.5 Induced sputum

Induced sputum will be collected from all cases except those with contraindications, which include the following: severe hypoxia (<92% on supplemental oxygen), inability to protect airways, severe bronchospasm at admission, seizure within the past 24 hours, or deemed inappropriate by a study clinician for another reason (e.g. mid-face trauma, inhalational injury, pulmonary edema, congestive heart failure, congenital heart disease, etc). If the above symptoms resolve during hospital course, induced sputum collection may be reconsidered at that point.

The following guidelines will be utilized for the collection of induced sputum.

- Sites will use Metered Dose Inhalers (MDIs) for bronchodilation
- Sites will employ light chest percussion in children < 2 years to improve mobilization of sputum. In children > 2 years, their cough reflex should be sufficient to mobilize sputum after induction with nebulization of hypertonic saline
- The specimen should optimally be collected within 24 hours. After 24 hours, induced sputum can still be collected (to test for tuberculosis and *Pneumocystis jiroveci*), but bacteriology should not be performed unless antibiotic therapy fails.
- The quantity of the specimen should be at least 1 mL.
- The quality of the specimen will be assessed using the "Bartlett's Score". Specimens with suboptimal Bartlett's Score will still be processed by the lab for all specified testing, but the Bartlett Score and consequent microbiology results will be considered in the analysis. Suboptimal Bartlett Scores will also be reported to the clinical team doing the procedure as a performance indicator.
- Some sites will perform a second induced sputum to improve the diagnostic yield for tuberculosis, as has been shown in other studies (Zar et al. 2005). This will be stipulated in site specific appendices.

4.5.1.6 Urine

Urine samples will be collected from cases and controls for two purposes: (i) to examine for the presence or absence of antibiotic activity, a marker of recent administration of antibiotics which might influence the sensitivity of culture-based microbiological techniques and (ii) to be stored for future examination of antigens that determine etiology and relevant urinary biomarkers (e.g. biomarkers of smoke/air pollution exposure and urinary arsenic). Urine will be taken at the

Version 6.0_15Nov2013

earliest opportunity from children admitted as cases, ideally before the first dose of antibiotic therapy. However, antibiotic infusions will not be delayed to obtain a urine sample uncontaminated with hospital-administered antibiotics. If the urine specimen is not obtained by this time, antibiotic administration should begin. The specimen can still be collected and analyzed for detection of antigens.

For infants and young children, urine will be collected into a perineal adhesive bag and transferred to a sterile universal container. Older children may pass urine directly into a sterile universal container. If antibiotics have been given by the nursing or medical staff prior to capturing the specimen then the specimen data collection form will be documented appropriately and the sample container will also be marked. Samples will be taken to the laboratory and stored immediately at 4-8 °C until processed.

4.5.1.7 Gastric Aspirates

Gastric aspirate will be collected from all children for whom an induced sputum cannot be collected at the time of enrollment (with timing of collection based on clinical judgment). The general technique used for gastric aspirates is to insert a nasogastric tube through the nose into the stomach, and gently aspirate the tube with a syringe until the child produces enough liquid for collection. This is uncomfortable for the child insofar as a small tube is passed through the nose into the posterior pharynx and then in to the stomach. This is a routine, daily procedure in all hospitals and is used for a variety of purposes including feeding children, decompressing the stomach of gas when in respiratory distress and collection of gastric contents. There is very little risk associated with the procedure except some discomfort at the time of tube placement and the low risk of inadvertently passing the tube into the trachea and not the esophagus. This is readily recognized clinically, the tube is withdrawn and placement attempted again.

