Hospitalized patients 28 days-59 months of age with severe pneumonia.

Controls:

Children from the community without severe or very severe pneumonia who are frequency matched to cases on age and season. HIV+ controls at sites with high HIV prevalence (Zambia and South Africa) will be selected from patient support centers (PSCs) serving the hospital catchment area.

Specimens:

Multiple specimens will be obtained from each case and control:

- Acute blood
- Convalescent blood (cases only)
- Nasopharyngeal and oropharyngeal swabs
- Induced sputum or gastric aspirate if sputum is not obtained (cases only)
- Pleural fluid (cases only, when clinically indicated)
- Lung aspirates (cases only, in select sites)
- Urine
- Post mortem lung needle biopsy (fatal cases only, in select sites)

Follow-up:

A limited clinical evaluation of the cases will be conducted 24 and 48 hours after admission. All cases will also be followed up 30 days (window 21-90 days) post-admission to assess mortality status and to collect convalescent blood and a urine specimen at select sites. Collection of ancillary study data and verification of household environmental risk factors may also be

conducted at this time. Weight and height may be collected in some sites at the follow up visit to assess the impact of pneumonia on acute growth parameters.

Diagnostic tests:

We plan to use bacterial and mycobacterial culture and several highly sensitive non-culture based laboratory diagnostic tools to test the different specimens collected from each child (see 4.6.4 Laboratory Evaluation).

Data structure:

The observed data can be envisioned as a four-dimensional matrix of subjects (cases or controls), specimens, tests and pathogens.

Analysis:

PERCH will estimate (1) the prevalence of infection for each of approximately 30 specific pathogens among cases hospitalized with severe pneumonia and (2) the frequency of each of these pathogens as a putative cause of hospitalized, severe pneumonia. It will also estimate the proportion of cases with no pathogen identified. This "unknown" group will be a high priority for pathogen discovery efforts.

Sample size:

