4.5.1.8 Pleural Fluid

Pleural fluid will be collected from a minority of cases as indicated by attending clinicians. These specimens will be used for bacterial culture, TB studies, and testing by PCR. The methodology for obtaining pleural fluid will follow local clinical practice guidelines, including standard safety precautions.

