*Indicates tests done as part of clinical standard of care. All sites except the Mali site collect blood for culture and complete blood count on hospitalized pneumonia cases. HIV and malaria testing is done as standard of care in sites where they epidemiologically relevant. Gastric aspirates and pleural taps are standard of care when clinically indicated. Lung aspirates will be collected for clinical care and research; specimens will be tested in real time for clinical use purposes. All other tests will be done for research.

**CD4 results are for analysis purposes only; will not be used for clinical care.

+Indicates tests that may directly impact the child's care, or have some other benefit

Note: Some sites may utilize regional reference facilities for TB and HIV testing rather than doing this testing at the study site labs themselves. Details will be included in the site specific appendices. HIV antibody tests may done on either serum or plasma based on local protocols.

Table X. Laboratory Evaluations of Controls								
Specimen	Subjects	Collection Container	Assay	Timing	Archive Sample	Centralized/ Decentralized Testing	Report results to parents	
			Pneumococcus PCR	Batch		Decentralized	No	
			HIV rapid antibody test(and follow-up PCR for positive in children < 18 months) † in selected sites only	Real time		Decentralized	Yes, in sites that do this test	
		EDTA Tube (plasma)	CD4 Testing (HIV+ controls, South Africa and Zambia only)*	Real time	Yes	Decentralized	Yes	
Acute Blood	All		Sickle Cell Testing(selected sites) †	Batch		May be centralized	Yes, in sites that do this test	
			Malaria antigen testing or microscopy (selected sites) †	Real time		Decentralized	Yes, in sites that do this test	
			Thalassemia (Thailand only) +	Real time		Decentralized	Yes, in Thailand	
			Hemoglobin (selected sites only)	Real time		Decentralized	Yes, in sites that do this test	
		Plain Tube	Biomarkers	Batch	Yes	Some may be centralized	No	

Table X. Laboratory Evaluations of Controls									
Specimen	Subjects	Collection Container	Assay	Timing	Archive Sample	Centralized/ Decentralized Testing	Report results to parents		
		(Serum)	Storage for future serologic testing	Batch		Centralized	N/A		
			Host Genetic Studies	Store		Centralized	No		
			Antibiotic activity	Batch		Decentralized	No		
NP flocked swab	All	Viral Transport Medium	PCR for respiratory pathogens	Real time	Yes	Decentralized	Yes, in selected sites		

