Because this is an observational study and does not involve an intervention, the main safety considerations in PERCH pertain to the collection of body fluids from cases and from controls. For cases, many of the body fluid collection procedures are already conducted as part of local, routine clinical care of patients hospitalized with severe or very severe pneumonia. Table XI below describes which **body fluids** are collected from **cases** as part of routine care and which are collected only for research purposes. Table VIII in section 4.6.4 indicates which **lab tests** on these body fluids are for research and which are part of standard care. Among **controls**, all body fluid collection is for research only.

For specimens that are part of clinical standard of care, procedures will conform or exceed the safety and proficiency methods already in use at the sites. Efforts will be made to standardize the method of collection and equipment used for collection across sites which will both enhance safety for the subjects and will lead to more robust study results. The PERCH Clinical Standardization physician will provide training to sites when procedures differ from routine standard of care. Only those personnel who have been confirmed/certified to have proficiency

in the study procedure will collect specimens. That confirmation will be done by the site PI or his/her designee.

	Table XI. Body fluid specimen collection among cases				
Body Fluid Specimen	Clinical Standard of Care or Research	Tests being done on this specimen that will benefit the participant (with respect to acute clinical care)	Activities to minimize risk		
Blood (all sites)	Standard of care. All sites consider blood cultures on hospitalized pneumonia cases as a component of routine care, not research.	 Blood culture Complete blood count HIV test Sickle Cell testing (selected sites) Malaria test (selected sites) 	 Limit volume to locally approved volume Collected by trained, proficient, personnel Sterile, single use equipment used Follow SOP 		
Urine (all sites)	Research	• None	 Sterile, single use equipment used Follow SOP 		
Gastric aspirates (all sites)	Standard of care when clinically indicated	• TB culture	 Collected by personnel who have been trained according to hospital guidelines Single use equipment used 		

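### Gastric aspirate is taken under a study rule when sputum is missing, yet it is labelled standard of care on clinical indication and serious events after it are not defined SAEs

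*Protocol*

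**What the plan says.** The collection rule appears twice. The specimen list in section 2.3 has "Induced sputum or gastric aspirate if sputum is not obtained (cases only", and section 4.5.1.7 has "Gastric aspirate will be collected from all children for whom an induced sputum cannot be collected at the time of enrollment". Section 4.5.1.7 leaves only the timing to clinical judgment.

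The classification appears three times, with a different sense:
- Table IX footnote (section 4.5.4): "Gastric aspirates and pleural taps are standard of care when clinically indicated".
- Table XI (section 5), gastric aspirate row: "Standard of care when clinically indicated". The safeguards listed there are single-use equipment and "Collected by personnel who have been trained according to hospital guidelines".
- Section 5.5 groups gastric aspirates done on clinical indication with pleural taps and blood draws, as routine standard of care.

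On hazards, section 4.5.1.7 mentions "the low risk of inadvertently passing the tube into the trachea and not the esophagus". Section 5.5 adds minor hemoptysis and aspiration, at very small risk.

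On reporting, section 5.7.1 defines SAEs for two groups only: children with a lung aspirate and children with an induced sputum. Section 5.6 limits the reporting of deaths as SAEs to the same two procedures. A general clause in 5.6 and 5.7.2 adds other events that are serious, related to study procedures and unexpected.

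**The concern.** An aspirate taken only because sputum was not obtained is done for the study. Describing it as indication-driven standard of care gives an ethics committee two accounts of why the child has the tube. Section 8.1 rests part of the risk-benefit argument on specimens being either routine care already or of minimal risk, so the label is material to that review.

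Separately, the children sent to the fallback include those in whom sputum induction was judged unsafe. The contraindications in section 4.5.1.5 include "severe hypoxia (<92% on supplemental oxygen), inability to protect airways, severe bronchospasm at admission, seizure within the past 24 hours". Section 4.6 says children with contraindications tend to be the sickest. A child with an unprotected airway may therefore have a nasogastric tube under a study rule with less defined safety reporting than the sputum induction would have carried. A death or serious aspiration soon afterwards could be absent from the monthly SAE reports that the Safety Monitor reviews.

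**Working it through.** The protocol gives no figure on this point, so the check sets the texts side by side.

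1. **Is a clinical indication needed?** No. Sections 2.3 and 4.5.1.7 use the absence of sputum as the only trigger. The next subsection, 4.5.1.8, shows how the protocol words a specimen that does depend on indication: "Pleural fluid will be collected from a minority of cases as indicated by attending clinicians". The Table IX footnote puts both procedures under one label, which fits the pleural tap but not the fallback aspirate.

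2. **Which cases does the rule reach?** Cases without induced sputum at enrollment, with one exception. For children whose case-defining signs resolve after bronchodilator, section 4.1.2 omits induced sputum and does not list gastric aspirate among the specimens to collect. Parents may also refuse any single specimen (section 8.1).

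3. **Is an event after a fallback aspirate a defined SAE?** Not through the aspirate itself, since 5.7.1 has no entry for it. It can be one through another procedure. After a lung aspirate, any in-hospital death counts. After a later induced sputum, death or defined deterioration within 4 hours counts.

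4. **Which route applies?** For a defined SAE, section 5.7.2 names the Local Safety Monitor, the data coordinating center, the PERCH Safety Monitor, the PERCH PI and the IRB, and the data coordinating center compiles monthly reports. For the general clause, 5.6 names no recipient, and 5.7.2 has the PERCH PI report to the IRB. Neither assigns the event to the Local Safety Monitor, the data coordinating center or the Safety Monitor.

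5. **Would the general clause catch the event?** Only if it is judged serious, related and unexpected together. Section 5.5 already lists aspiration as a risk, so a site could judge it expected. The standard-of-care label also makes relatedness to a study procedure easier to deny.

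6. **Is there surveillance?** Table XI asks for 4 hours of monitoring for deterioration after induced sputum and after lung aspirate. It asks for none after gastric aspirate. Section 5.6 justifies active surveillance of the first two on the ground that they are not standard of care in every setting, and a tube placed only under the fallback rule fits that reason.

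**The case against.** The strongest reply is that the SAE scope follows the protocol's own risk ranking. Section 5.5 puts only pleural tap, among blood draws, gastric aspirates and pleural taps, above minimal risk, and even pleural tap has no entry in 5.7.1. Section 4.5.1.7 calls the procedure routine in all hospitals and says a misplaced tube is readily recognized and withdrawn. Timing rests with the clinician, so an unstable child need not have the tube at once. Sections 5.7.2 and 5.8 also provide for reporting unanticipated events and let either the PERCH PI or the site PI pause activities. All of this stands, and it keeps the point small. It does not remove the conflict in wording, nor does it assign these events to the safety bodies.

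A reader might infer more than the documents support:
- **That these events cannot be reported at all.** The general clause still reaches the IRB, and some children are covered through a lung aspirate or a later induced sputum.
- **That the label caused the omission.** Swabs and urine are labelled research and have no SAE criteria, while lung aspirate is covered even where it is routine. Label and SAE scope do not move together.
- **That ethics committees were kept from the fallback rule.** Sections 2.3 and 4.5.1.7 state it openly, so the fault is inconsistency.
- **That counting named hazards against SAE criteria, compared with lung aspirate, measures the gap.** Such counts depend on which hazards are included and show nothing about risk.

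**Conclusion.** The point holds in a limited form. Fallback gastric aspirates are a study procedure described in three places as indication-driven standard of care. Serious events after them fall outside the defined SAEs and the named safety route, unless another covered procedure brings them in.

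The size cannot be given as a number: the protocol states neither how many children will have a fallback aspirate nor how many of those would have had one clinically anyway. The stated risk per procedure is very small. The etiology analysis, power and type I error are not affected. The case for change rests on the vulnerability of part of the fallback group and on the low cost of closing the gap. The wording conflict is certain from the text. That the general clause might miss an event is a judgment about how sites would apply the requirement that it be unexpected.

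**What to change.** - In Table XI, the Table IX footnote and section 5.5, class an aspirate done only under the fallback rule as a study procedure. Keep the standard-of-care label for one done on clinical indication.
- In sections 5.6, 5.7.1 and 5.7.2, add for children with a fallback aspirate: any death within 4 hours; and any tracheal misplacement or aspiration with clinical deterioration from the pre-procedure state within 4 hours. Send these through the existing SAE route, graded for relatedness as for other SAEs.
- Define deterioration against the child's recorded state before the tube. Do not copy the induced sputum criteria on 92% saturation and bronchodilator use, because some of these children are already below 92% on oxygen or have severe bronchospasm.

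The fallback rule stays, so no tuberculosis specimens are lost. The cost is a protocol amendment, a short note of the child's state before the procedure and over the next 4 hours, and a few extra SAE reports. Some of those reports will reflect the disease and not the tube, which is why the relatedness grading is needed.
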